6. DEVICE INFORMATION

6.1 Availability

The RESPeRATE devices are easily available and do not require any sort of prescription or permission to purchase.

6.2 Device Request and Distribution for Sites

Devices will be distributed to the sites from Wake Forest NCORP Research Base when the study is IRB approved at their site. Upon completion of the last participant, the site will return the RESPeRATE devices to the Wake Forest NCORP Research Base. See Section 6.6 for more information.

6.3 Device Accountability

Not applicable. The intervention is a simple and publicly available device. It is not a drug agent.

6.4 Registration/Randomization

6.4.1 Registration Process

An IRB letter of approval and an IRB approved consent form must be received by the Research Base Protocol Information Office – Attn: Site Coordinator prior to patient registration. [contact]

Fill out Appendix 2, Eligibility Checklist / Registration Form, and use this to complete the online registration.

Online Registration

NCORP site staff will register their study participants into the WF NCORP RB database by following the instructions below:

Log on to the WF NCORP Research Base registration web site at <https://ccrbis.phs.wakehealth.edu>. Enter your username and password (which may be obtained by contacting [name] RN OCN at [contact]). In the “Patient Registration and Protocol Information” table, click “Register Patient/Patient Info” with the corresponding protocol number found in the drop-down box to the right. Fill in the eligibility criteria forms using the drop-down boxes. If further information is needed by Data Management, they will contact you. Once the patient information has been entered online, print a copy of the eligibility checklist/registration form for your records. Press the submit button and a confirmation page will appear. Print this confirmation sheet for your records. The WF

NCORP Research Base Online Protocol Registration/Eligibility form, initial flow sheet, signed consent, histology reports, scan reports and lab reports (as required in protocol) should be faxed to [contact] or mailed to Data Management:

Wake Forest School of Medicine
Department of Social Sciences and Health Policy
WF NCORP Research Base
Data Management Center
[name]
[name]
[name]
[name]

These forms should be retained in the patient's study file. These forms will be evaluated during an institutional WF NCORP Research Base site member audit.

If you have questions related to the registration process or require assistance with registration, please contact the WF NCORP Research Base DMC between 8:30am and 4:00pm EST, Monday through Friday at [contact] or [name].

6.4.2 Randomization Process

Patients will be stratified by baseline dyspnea score (Cancer Dyspnea Scale score ≥ 8 v. < 8 ; see Table 7.8) and assigned with equal probability to either RESPeRATE intervention group or the control group using variable length permuted block randomization. Block sizes will be chosen randomly to ensure that future assignments cannot be inferred from previous ones. Patients need to report a minimum level of clinically significant anxiety symptoms (HADS-Anxiety/Depression Scale anxiety subscale ≥ 8), cancer-related worry (Modified Cancer Acceptance Scale score > 5), or distress (Distress Thermometer ≥ 4) to enter the study.

6.5 Unblinding Methods

Not applicable.

6.6 Device Return

Study participants will return any study devices to the site that issued them. All sites must return study devices to the Wake Forest NCORP Research Base at the following address:

[name], OCN
Wake Forest School of Medicine
Department of Social Sciences and Health Policy
NCORP Research Base – [name]
[name]
[name]
[name]

7. CLINICAL EVALUATIONS AND PROCEDURES

7.1 Schedule of Events

Participants will be randomized to one of three groups: RESPeRATE device-guided breathing group (low-dose) (n=25), RESPeRATE device-guided breathing group (high-dose) (n=25), and a usual breathing control group (n=25).

The low-dose group will use the RESPeRATE device for 15 minutes once a day, at least 5 days per week for 12 weeks.

The high-dose group will use the RESPeRATE device for 15-minutes twice a day, at least 5 days per week for 12 weeks.

The usual breathing control group will use an identical control device (with nonrhythmic tones that will not gradually slow down to reduce respiration rate) for 15 minutes once per day, at least 5 days per week over 12 weeks.

After randomization, participants will be introduced to their assigned device and receive instructions and a demonstration on use. Participants will use it at least 5 days per week for the assigned amount of time over 12 weeks. All participants will complete pre- and post-intervention questionnaires, spirometry (FEV1) at baseline and Week 12, weekly telephone contact to provide breathing data for the prior 7 days, brief mid-intervention questionnaires by mail with a stamped return envelope enclosed and/or telephone contact at Week 6, and rate symptom intensity while using the devices (before and after one session per week). Eligible participants will collect salivary cortisol samples for three days following baseline and the Week 12 follow-up. Participants with endocrine disorders (e.g., diabetes and thyroid disorders) or on steroid-based medications (topical steroid medications are permitted) are excluded from the cortisol portion of the study. Participants will have a blood draw at the baseline and 12 week visits, to determine if RNA and/or DNA methylation and/or gene expression variation correlates with anxiety changes. The duration of the study is 12 weeks.

The NCORP staff member will instruct each participant in use of the RESPeRATE device at baseline. Participants will be told that RESPeRATE analyzes a person's breathing pattern and plays 2 distinct tones that guide the person to inhale and exhale. The RESPeRATE control device looks and sounds identical but is not programmed to gradually slow breathing rate as in the active intervention arm. All participants will be provided with written instructions for the assigned device and will be observed using the device during the visit. To enhance adherence, we will have a NCORP staff member call participants weekly to assess experience with the device, troubleshoot difficulties that may have arisen and obtain breathing data for the prior 7 days. Participants who have not been using the device at the recommended frequency will troubleshoot ways of overcoming barriers to adherence as needed.

Self-reported dyspnea and spirometry (FEV1) include questionnaires and a pulmonary function test (PFT). These measures will be administered in-person at the NCORP site during baseline and post-intervention (Week 12) assessments. A shorter battery will be administered mid-intervention via mailed paper questionnaire with a stamped return envelope enclosed (Week 6). Any serious adverse event grade 4 or 5 related to the intervention will be reported to the WF NCORP RB at the time they become known to the NCORP site. (See Section 10.0)

7.2 Pre-Screening Evaluation/ Baseline Testing

Pre-Screening:

A minimal score on one of three measures is required for study eligibility. These measures include: (1) Score > 5 on the Modified Cancer Acceptance Scale (two-item screener) OR (2)

Score ≥ 4 on the Distress Thermometer OR (3) Score of ≥ 8 on the anxiety subscale of the HADS-Anxiety/Depression Scale.

- The single-item Distress Thermometer is a brief, single-item screening tool assessing distress from 0 (no distress) to 10 extreme distress). Recent meta-analyses have identified a score ≥ 4 as an appropriate cut-off for identifying significant levels of distress.
- The Modified Cancer Acceptance Scale assesses fear of disease recurrence and consists of 2 items: “I worry about the cancer returning” and “I am anxious about my health.” Both items are rated on a 4-point Likert scale ranging from “does not apply to me at all” to “completely applies to me.” Scores range from 2 to 8.
- The full HADS (including the depression subscale) will be administered either over the phone or in person. Scores will be used as the baseline value to minimize burden by administering the measure again within a short time interval. The HADS-Anxiety/Depression Scale is a 14-item self-report measure that is scored by assigning a numeric value to each of the 14 items (0, 1, 2, or 3), and then totaling item scores. The minimum score is 0 and the maximum score is 42. Anxiety and depression subscales each consist of the sum of 7 questions (range 0-21 for each subscale). A score ≥ 8 on the anxiety subscale indicates significant anxiety. Some items may be left blank. In this case, scores will be calculated as long as more than half the items are answered. The scores will be calculated as the mean of the responses times the number of items in the scale (7 for the subscales and 14 for the overall scale).
- Eastern Cooperative Oncology Group performance status 0-2.

Baseline testing:

- Hospital Anxiety/Depression Scale (HADS) (use form completed for screening)
- Cancer Worry Scale
- Cancer Dyspnea Scale (CDS) **will be needed for registration**
- PROMIS Fatigue
- Manchester Cough in Lung Cancer Scale
- Activities form
- Current medications
- Participant expectations rating
- Spirometry (forced expiratory volume in one second [FEV1])
- Visual Analogue Scales (VAS) for distress, anxiety and dyspnea—this form should be completed once a week before and after a single use of the device during Weeks 1-12
- Blood draw—a blood sample of approximately 2 teaspoons will be taken from a vein in the arm/central line for DNA methylation levels and RNA.
- Salivary cortisol collection—saliva samples will be collected by participants at time of awakening, 30 minutes post-awakening, and at bedtime for three consecutive days (9 samples per participant).

7.3 Evaluations during Study Intervention at Weeks 1 - 11

Weeks 1 - 11:

- Weekly Check-in Call/Data Capture from Device via telephone interview. The participant will be contacted by phone to assess his/her experience with the device and troubleshoot difficulties that may have arisen and obtain breathing data for the prior 7 days. The participant will also be asked if (s)he completed the once weekly

VAS for distress, anxiety, and dyspnea (before and after a single use of the device each week). If (s)he has not done so, (s)he will be asked to complete the VAS form before and after their next use of the device. Participants who have not been using the device at the recommended frequency will troubleshoot ways of overcoming barriers to adherence, as needed.

Week 6:

- In addition to phone contact, participants are to complete the following questionnaires (may be done via mail):
- Hospital Anxiety/Depression Scale (HADS)
- Cancer Worry Scale
- Cancer Dyspnea Scale
- PROMIS Fatigue
- Manchester Cough in Lung Cancer Scale
- Activities form
- Weekly Check-in Call/Data Capture from Device Form (via telephone)

7.4 Evaluations at Completion of Study Intervention

Week 12:

- Hospital Anxiety/Depression Scale (HADS)
- Cancer Worry Scale
- Cancer Dyspnea Scale (CDS)
- PROMIS Fatigue
- Manchester Cough in Lung Cancer Scale
- Activities form
- Current medications
- Collect Weekly Check-In Call/Data Capture from Device forms
- Intervention feedback
- Spirometry (forced expiratory volume in one second [FEV1])
- Visual Analogue Scales (VAS) for distress anxiety and dyspnea
- Blood draw—a blood sample of approximately 2 teaspoons will be taken from a vein in the arm/central line for DNA methylation levels and RNA.
- Salivary cortisol collection, if applicable—saliva samples will be collected by participants at awakening, 30 minutes post-awakening, and at bedtime for three consecutive days (9 samples per participant)

7.5 Methods for blood draw and transport

7.5.1 For detection of DNA methylation levels:

Genomic DNA will be isolated from whole blood (one 8/8.5 ml yellow-top, ACD tube). DNA will be isolated using the AutoPure LS (Qiagen, Inc.), and then bisulfite-converted using the EZ DNA Methylation Gold kit (Zymo, Irvine, CA). To determine the proportion of DNA methylation at each of over 485,000 CpG sites, we will use the HumanMethylation450 BeadChip (Illumina, Inc.) along with the iScan Reader (Illumina, Inc.).

7.5.2. RNA:

RNA will be isolated from whole blood collected in one 2.5/4 ml tube using the PAXgene Blood RNA System (Qiagen), following the manufacturer's instructions. The PAXgene system stabilizes the RNA and minimizes degradation, a process that can lead to false results in

subsequent analysis. As with the DNA, the whole blood for RNA will be stored with the tube upright at room temperature until transported to the laboratory. RNA will be isolated with the PAXgene Blood RNA System (Qiagen), following the manufacturer's instructions. Once isolated, RNA will be evaluated for quality and quantity using the RNA 6000 Nano chips and analyzed on the Agilent 2100 Bioanalyzer (Agilent Technology, Inc). Expression profiles will be generated with HumanHT-12 v4 Expression BeadChips (Illumina, Inc.), which assay over 47,000 probes spanning approximately 30,000 genes. BeadChips will be scanned with the iScan Reader (Illumina, Inc.), and preliminary analysis will be performed with Genome Studio (Illumina, Inc.).

Blood samples will be collected at baseline and Week 12. Once collected, [name] lab will be notified by phone at [contact]. Samples will be processed and shipped per instructions in Appendix 19.

7.5.3. Methods for cortisol collection, assays, and mailing:

Participants with endocrine disorders (e.g., diabetes and thyroid disorders) or on steroid-based medications (topical steroid medications are permitted) are excluded from the cortisol portion of the study.

Materials for saliva collection will be distributed to participants at baseline. Materials can be provided in-person at the clinic visit or the materials can be shipped to the participant's home. Participants will collect saliva samples three times a day (at awakening, 30 minutes post-awakening, and bedtime) for three consecutive days following baseline and three consecutive days following the Week 12 follow-up visit. Saliva samples are collected by placing a cotton roll under the tongue for approximately 1-2 minutes which is subsequently stored in a plastic tube and refrigerated. Participants will be instructed to refrain from eating, drinking, smoking, brushing their teeth, using mouthwash, or engaging in exercise or similar physical activity for 30 minutes prior to saliva collection. Participants will be provided with saliva collection diaries to record compliance to these behaviors as well as the time in which their saliva samples were collected. After all nine samples have been collected at each time point (baseline, Week 12 follow-up), participants may return their samples and saliva collection diaries by: 1) returning them to the local clinic within 2 weeks of collection and the local clinic will take responsibility for sending them to Wake Forest NCORP Research Base, or 2) using pre-paid postage to return their samples and saliva collection diaries directly to the Wake Forest NCORP Research Base. Once received at the Wake Forest NCORP Research Base, all samples will be refrigerated (-80° C) until assayed.

Samples will be assayed in duplicate at Wake Forest NCORP Research Base using The Salimetrics® Cortisol Enzyme Immunoassay Kit (State College, PA). At no time in the testing process are samples identified by name of subject or any information that would link the sample directly to an individual. On the day of analysis, samples are thawed at room temperature (20 to 22°C), centrifuged (1500 x g) for 15 minutes and assayed. The test used 25 µL of saliva per determination, has a lower limit of sensitivity of 0.003 µg/dL, standard curve range from 0.012 µg/dL to 3.0 µg/dL, an average intra-assay coefficient of variation of 3.5% and an average inter-assay coefficient of variation of 5.1%. Method accuracy determined by spike and recovery averaged 100.8% and linearity determined by serial dilution averaged 91.7%. Values from matched serum and saliva samples show the expected strong linear relationship, $r (47) = 0.91$, $p < 0.0001$.

Samples are returned to the freezer upon completion of pipetting. Assay data are reviewed by the supervisor and samples needing to be retested are identified. Samples needing retesting are again thawed, analyzed and refrozen. After assays are complete, samples will be stored for up to 60 days and then disposed of per applicable waste handling regulations.

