Site coordinators will contact participants on a weekly basis by phone to assess use of the device, answer questions, and collect breathing data for the prior 7 days stored on the device.

Week 6 (mid-intervention) Data Collection

In addition to the device breathing data, the following forms will be completed by phone and/or mail. Brief questionnaires to include Self-Reported Dyspnea Anxiety/Depression/Cancer-Related Worry, Fatigue, and Cough Questionnaires.

Week 12 Data Collection

Participants will be seen in the clinic for collection of final breathing data and to complete measures: Self-Reported Dyspnea, Spirometry (FEV1), Anxiety/Depression/Cancer-Related Worry, Fatigue, Cough Questionnaires, blood draw, and salivary cortisol collection. Participants will return their RESPeRATE device to the site coordinator.

Endpoints

Feasibility (accrual, participation, adherence, retention), Anxiety, Cancer-Related Worry, Self-Reported Dyspnea, Spirometry (FEV1), Epigenetic and Gene Expression Changes, salivary cortisol changes (for those who are eligible related to Supplemental Objective 1.5)

Stratification: Site; Self-Reported Dyspnea

Study Sample: 75 participants (25 per group)

Study Duration: 12 weeks

Brief Eligibility Criteria:

- Past History of any lung cancer
- For Stage I-III disease, patients should be 2-24 months post-completion of surgery, radiation therapy and/or chemotherapy with no further planned treatment during the 12-week study and no evidence of disease.

For Stage IV disease, patients may be receiving no treatment or may be receiving maintenance treatment with a target agent, chemotherapy, or immunotherapy provided the most recent imaging does not demonstrate progressive disease.

- After completion of all three screening questionnaires, participant must score accordingly on at least one questionnaire to be eligible:
 - score ≥ 8 on the anxiety subscale of the HADS ¹ OR
 - score ≥ 4 on the Distress Thermometer ⁹²⁻⁹⁴ OR
 - score > 5 on the Modified Cancer Acceptance Scale ⁹⁶
- Eastern Cooperative Oncology Group performance status 0-2

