The proposed device-guided breathing intervention works by gradually slowing the respiration rate. Slow, deep breathing enhances parasympathetic tone, decreases acute and chronic sympathetic arousal, and reduces excitatory nervous activity, likely through cellular signaling activated by stretch receptors in the lungs.⁵⁹

The relaxation response occurs acutely, but indicators of chronic sympathetic over-activation, such as resting hypertension, also decrease. Deep breathing improves respiratory and cardiovascular function, decreases effects of stress, and improves mental health.¹ Disordered

respiration is thought to be a key aspect of anxiety and stress-related disorders,^{34,37} thus slow breathing also reduces anxiety and potentially dyspnea.^{60,61}

Participants in the usual breathing control group will use an identical-looking device but only the RESPeRATE intervention is targeted at reducing respiration rate. The chimes for the control device will be nonrhythmic tones that will not gradually slow down to reduce respiration rate. A similar control device is available from the same company and has been employed in other studies of the RESPeRATE device.¹⁰⁴

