3. SUMMARY OF STUDY PLAN

The RESPeRATE device constantly synchronizes and automatically adjusts the melody/tones to the person's breathing pattern to reduce breaths per minute by prolonging exhalation. It is the size of a portable compact disc player with a respiration sensor.

This pilot study will have three groups: RESPeRATE device-guided breathing group (low-dose) (n=25), RESPeRATE device-guided breathing group (high-dose) (n=25), and a usual breathing control group (n=25).

The low-dose group will use the RESPeRATE device for 15 minutes once per day, at least 5 days per week for 12 weeks.

The high-dose group will use the RESPeRATE device for 15-minutes twice per day, at least 5 days per week for 12 weeks.

The usual breathing control group will use an identical control device (with nonrhythmic tones that will not gradually slow down to reduce respiration rate) for 15 minutes once per day, at least 5 days per week over 12 weeks.

After randomization, participants will be introduced to their assigned device and receive instructions and a demonstration on use. Participants will use the device at least 5 days per week for the assigned amount of time over 12 weeks.

All participants will complete pre- and post-intervention questionnaires spirometry (FEV1) at baseline and Week 12, weekly telephone contact to provide breathing data for the prior 7 days, brief mid-intervention questionnaires (at Week 6), and rate symptom intensity while using the devices (before and after one session each week). Eligible participants will collect salivary cortisol samples for three days following the baseline and Week 12 follow-up. Participants will have a blood draw at the baseline and Week 12 visits to determine if RNA and/or DNA methylation and/or gene expression variation correlates with anxiety changes. The duration of the study is 12 weeks.

Participants will be stratified by baseline self-reported dyspnea score and assigned with equal probability to either intervention group or the control group using variable length permuted block randomization. Block sizes will be chosen randomly to ensure that future assignments cannot be inferred from previous ones.

Drs. [name] and [name] will meet with designated staff members from each NCORP site for a training session to review the protocol and provide intervention information. This training will take place at the annual meeting of the WF NCORP RB and/or at individual sites, as needed.

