Salivary Cortisol Analyses. Participants with endocrine disorders (e.g., diabetes and thyroid disorders) or on steroid-based medications are excluded from the cortisol portion of the study (topical hydrocortisone cream permitted). Cortisol levels will be assessed upon awakening, 30 minutes post-awakening, and at bedtime for three consecutive days at baseline and three consecutive days at 12 weeks. Several measures will be derived from the three daily cortisol values, including the mean levels at each time, the mean cortisol awakening response (CAR – change in cortisol from awakening to 30 minutes), the area under the curve (AUC), and the diurnal slope (change in cortisol between awakening and bedtime). Scatterplots and correlations will be used to quantitate the associations between these measures, and anxiety at each time (baseline and 12 weeks) as well as association between the change in cortisol measures and the change in anxiety. Additionally, mixed effects models, as described above, will be used to assess the association between baseline cortisol and changes in anxiety over time. To assess group differences in cortisol parameters, each of these measures at 12 weeks will be used as dependent variables in analysis of covariance models, using appropriate transformations as needed. Baseline levels of the measures will be used as covariates along with treatment group.

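### The final saliva set is collected after the device has been handed back, so the 12-week cortisol outcome measures the state just after stopping and is not aligned with the HADS-A it is correlated with

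*Combined protocol and SAP*

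**What the plan says.** Three sections agree on when the final saliva is collected.

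- Section 3: "Eligible participants will collect salivary cortisol samples for three days following the baseline and Week 12 follow-up".
- Section 7.1: "Eligible participants will collect salivary cortisol samples for three days following baseline and the Week 12 follow-up".
- Section 7.5.3: samples at awakening, 30 minutes later and at bedtime, on "three consecutive days following the Week 12 follow-up visit".

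The Schema, under Week 12 Data Collection, describes the visit itself: "Participants will be seen in the clinic for collection of final breathing data and to complete measures". The anxiety questionnaire, spirometry and blood draw are among those measures. The same paragraph ends: "Participants will return their RESPeRATE device to the site coordinator". It also lists saliva among the visit's measures, but a set with awakening and bedtime samples over three days cannot be completed in a clinic visit, so the three sections above govern.

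Section 12.5 treats the second set as cortisol on "three consecutive days at baseline and three consecutive days at 12 weeks". It correlates cortisol with anxiety at each time point and change with change. It also uses the 12-week cortisol measures as outcomes in analysis of covariance models for group differences. Section 7.6 plans no post-intervention follow-up.

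**The concern.** Supplemental objective 1.5 asks how cortisol changes in each group and how it relates to anxiety. Section 2.1c gives the hypothesis: anxiety changes attributed to the device go with cortisol changes. As scheduled, the two halves of that pair come from different treatment states. HADS-A closes 12 weeks with the device in hand, while cortisol is sampled after the device has gone back. The plan does not say this is intended, and Section 12.5 labels both measurements 12 weeks.

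At stake is the reading of a null result. If cortisol shows no group difference, or no association with anxiety, the plan cannot separate absence of effect from an effect that faded once use stopped.

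**Working it through.** **1. Sample count (the plan's own figure).** Section 7.4 gives 9 samples per participant at Week 12. Three collection times × three days = 9, so the figure reproduces.

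**2. Timeline.** Take the Week 12 visit as day 0.

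| Event | Source | Day |
|---|---|---|
| HADS-A, spirometry, blood | Schema, Section 7.4 | 0 |
| Device returned | Schema | 0 |
| Final saliva | Sections 3, 7.1, 7.5.3 | +1, +2, +3 at the earliest |

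The first sample of each day is at awakening, so the earliest full collection day after the visit is day +1. The mean lag is then (1 + 2 + 3) / 3 = 2 days. Samples taken while the participant holds the device: 0 of 9. No section extends device use through the saliva days or repeats the HADS on them.

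**3. How much of an effect could be lost.** The documents give no decay rate, so this step rests on an assumption. Suppose the on-device effect decays exponentially with half-life h days after return and collection starts on day +1. The average share remaining is

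share = [0.5^(1/h) + 0.5^(2/h) + 0.5^(3/h)] / 3.

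For h = 1: (0.500 + 0.250 + 0.125) / 3 = 0.292. The other values follow in the same way:

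| Assumed half-life (days) | Share remaining | An illustrative 0.5 SD difference is seen as |
|---|---|---|
| 1 | 29% | 0.5 × 0.292 = 0.15 SD |
| 3 | 64% | 0.5 × 0.641 = 0.32 SD |
| 7 | 82% | 0.5 × 0.823 = 0.41 SD |
| 14 | 91% | 0.5 × 0.906 = 0.45 SD |
| 28 | 95% | 0.5 × 0.952 = 0.48 SD |

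The 0.5 SD is only a convenient scale, since the plan states no expected cortisol effect. A wholly lasting effect loses nothing, and a wholly session-bound one could be lost almost entirely. A later start than day +1 would increase the loss.

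**4. What the protocol says about persistence.** Section 2.3 supports both ends of the range: "The relaxation response occurs acutely, but indicators of chronic sympathetic over-activation, such as resting hypertension, also decrease". It offers no basis for choosing a half-life.

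**The case against.** The strongest reply is that this is a legitimate design choice. Section 7.4 files the saliva under evaluations at the end of the intervention. All three arms return the device at the same visit, so the comparison is between like and like and estimates the effect just after a 12-week course. The measures are daily-rhythm summaries, not taken around a session. Use is required on only 5 of 7 days, so up to 2 days a week without a session are already allowed during the intervention. Nothing bars a session on the visit day before the device goes back, so the first morning's samples could follow a session within a day.

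Most of this stands. The randomised comparison is not confounded, and the contrast is between days when a session is possible and days when it is not, which is milder than daily use against none. What the reply does not answer is the mismatch with HADS-A, or the fact that Section 12.5 nowhere says its outcome describes the state after device return.

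A reader might go further and infer that the cortisol comparison is biased toward no effect. The documents do not support that. Such a bias exists only relative to an on-intervention effect, and only if the effect fades within days, which no section states. A reader might also infer that collection could drift well beyond the visit. Section 7.5.3 sets no start day, but its wording reads naturally as immediately after the visit. Appendix 18, which holds the saliva instructions, is not in the supplied text, and the diary records collection times.

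Moving the final set has one further consequence. The baseline set stays after the baseline visit, so the two sets would no longer sit on the same side of their visits. However, the Schema has the device issued and first used at the baseline visit. Today the change score therefore compares device-in-hand days with device-returned days; after the move, both sets fall on device-in-hand days.

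**Conclusion.** The point holds as a matter of timing and labelling. All nine final samples fall after device access ends, while the paired HADS-A is taken at the visit. What is estimated is cortisol just after stopping. Dilution of any part of the effect that depends on current use runs from near zero to large, and the documents do not allow it to be narrowed. The 29% to 95% retained rests on assumed exponential decay, half-lives of 1 to 28 days and collection starting the day after the visit. The documents also state no recall period for the HADS, so the mismatch is one of days and device status, with no derivable numerical bias.

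Severity is low. Feasibility, the HADS-A comparison, dose selection and the rule for proceeding to phase III do not use cortisol. It is worth correcting because the correction is cheap and makes a null result for supplemental objective 1.5 easier to interpret.

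**What to change.** In Sections 3, 7.1 and 7.5.3, and in the saliva instructions (Appendix 18), schedule the final saliva on the three consecutive days immediately before the Week 12 visit. The coordinator prompts this at the Week 11 call, and participants hand in samples and diary at the visit. Bring the Schema and Section 7.4 into line.

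In Section 12.5, keep all sets in the main cortisol analysis. Use the diary's collection dates to flag any set collected after device return, and run a sensitivity analysis without the flagged sets. Do not drop them from the main analysis. That would be an exclusion after randomisation, in a subset already reduced by the endocrine and steroid criteria, and late collection may be related to adherence.

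If the schedule is kept as it is, Section 12.5 should at least state that the second cortisol measurement is taken after device return, and interpret objective 1.5 accordingly.

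The cost is a short amendment and a revised instruction sheet. No samples, calls or visits are added: Section 7.5.3 already distributes saliva materials at baseline, and Section 7.3 already has a Week 11 call. There are two downsides. Sites must make sure the Week 12 kit is in hand before the visit, and any sets already collected under the present schedule will differ in timing from later ones, which the flag handles.
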